6. MILESTONES

Milestone	Nordic Registries Study	U.S. Study	
	Anticipated Dates	Anticipated Dates	
Study protocol resubmitted to EMA	November 21, 2022	November 21, 2022	
Protocol approved by EMA	December 15, 2022*	December 15, 2022*	
Registration in EU PAS Register	January 15, 2023	January 15, 2023	
Apply for registry data for secondary	September 15, 2023 (post	N/A	
use	EC approval)		
Data receipt and start date for data	December 29, 2023	February 15, 2023	
analysis			
Interim report of study results #1**	April 15, 2024	N/A	
Interim report of study results #2***	April 15, 2025	N/A	
Final report of study results****	December 31, 2025**	August 4, 2023**	

^{*} Subsequent dates are dependent on timing of protocol approval by EMA

^{**} Based on counts of patients prescribed/dispensed Mysimba/Contrave through the end of 2021 and assuming both 80% are captured in the databases and 80% of identified patients are new users with at least 365 days continuous eligibility in data source before first Mysimba/Contrave prescription/dispensing, then there should be >3,000 eligible patients in data sources from US, Norway, Finland and possibly Sweden in this

analysis; it is uncertain at this time whether there will be at least 750 patients in Denmark during the conduct of the NB-451 study. Data for this interim study report will be the data available by December 29, 2023; it is likely that data will only be available through 2021 at this time.

*** A second interim report will only be included if Denmark identifies 750-3,000 eligible patients who would be available before December 31, 2024.

**** Final report date dependent on accumulation of data from the four Nordic country databases. Based on counts to date and projections of new users, there should be >3,000 eligible patients in the Norway and Finland data sources at the end of 2023. The 2023 data from Norway and Finland are expected to be available in late 2024. If final data are available in late 2024, the December 2025 final report will include the new final results from Norway, Finland, and Sweden, with updated interim or final analyses in Denmark, if appropriate.. Additionally, the final report will provide synthesis across all four Nordic data sources.

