To allow for multiple cycles of Mysimba/Contrave use and assessment of outcomes after initial exposure, the follow-up window for data collection after the index date will be up to 548 days (18 months), as an appropriate time-horizon for this specific purpose. All patient time during the follow-up window will be captured and censoring will occur at the earliest of death, disenrollment, 548 days of follow-up, or end of the study period (December 31, 2023).

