9.4.1.3. Norwegian Health Registries

The Norwegian Prescription Database (NorPD) includes data on all prescription drugs dispensed in Norway since January 1, 2004 and is controlled by the Norwegian Institute of Public Health (NIPH). Pharmacies electronically register prescriptions to the NorPD via Statistics Norway on a monthly basis. The residents' national ID number and the prescribing provider's ID number are

replaced by a pseudonym to link drug use to individuals and other registries data while protecting patient identity. The NorPD will be linked with other Norwegian Patient Registries with information that includes demographic information of the patient (sex, year of birth, and municipality of residence), place and time of treatment, diagnoses, medical procedures, and reimbursement information of medical care.

Based on current and projected Mysimba prescription counts as estimates obtained during the last annual feasibility assessment and reimbursement in Norway restricted to the morbidly obese, we anticipate that this database may include >3,000 new users of Mysimba who will be eligible for inclusion in the study as of December 31, 2023 (to be confirmed when data access is granted). A final analysis of the database will be conducted for the final report including all patients meeting the inclusion criteria for the study as of 31 December 2024 (final report available 31 December 2025).

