We anticipate that the US dataset will include >20,000 new users of Contrave who will be eligible for inclusion in the study as of December 31, 2022. The final analysis of the US database will be conducted and presented in a US only study report.

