9.7. Data Analysis

9.7.1. Timing of Feasibility, Interim, and Final Analyses

Prior to study start, feasibility was conducted annually.

One cohort per country will be extracted each time the database is opened. Per database, the following analyses will be conducted:

- 1. ongoing data review, for each of the participating Nordic countries
- 2. a first (interim) analysis when a database size reaches 750 patients with up to 548 days of activity in database after index date
- 3. a second (interim) analysis when an additional 2,250 patients (total 3,000 patients) with a Mysimba/Contrave index date are included in a database with up to 548 days of calendar time available in the database after the index date
- 4. a final analysis of the database will be conducted for the final report including all patients from the EU data sources meeting the inclusion criteria for the study as of 15 February 2025. If >3000 patients are available at the time of an interim analysis, the final report for

that database will be submitted one year after data is accessible. If final data is available 31 Dec 2024, the final report will be submitted by 31 Dec 2025.

All analyses will be performed separately in each country. All patients in the study will be included in the analysis, regardless of whether there is evidence of any contact with the health system (as registered by any data in the database) after inclusion into the study. One interim and one final analysis will be conducted per country. A final report will be generated when the last database in the study conducts the final analysis (when the last database has >3000 Mysimba patients, or 31 Dec 2025, whichever comes first). The final analysis from the four participating Nordic countries will be included in that report which will be accompanied by synthesis of findings, discussion, and interpretation across all Nordic databases.

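### One censoring date, 31 December 2023, is set for every database: it cannot operate in the US source and is not reconciled with the later Nordic inclusion dates

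*Protocol*

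**What the plan says.** **Censoring rule.** Protocol Section 9.3.2 says that "the follow-up window for data collection after the index date will be up to 548 days (18 months") and that "censoring will occur at the earliest of death, disenrollment, 548 days of follow-up, or end of the study period (December 31, 2023"). Figure 1 note c (Section 9.3.1) lists the same four events without a date. Inclusion criterion 1 (9.1.1) requires the qualifying prescription or dispensing to fall in the study period, and 9.3.2 is the only place that dates the end of that period.

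**US dates.** Section 6 anticipates US data receipt and start of analysis on "February 15, 2023" and the US final report on 4 August 2023. Section 9.4.2 anticipates more than 20,000 new users "eligible for inclusion in the study as of December 31, 2022".

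**Nordic dates.** Section 6 expects data only through 2021 for the first interim report. For the final report it says: "The 2023 data from Norway and Finland are expected to be available in late 2024". Section 9.4.1.3 describes a Norwegian final analysis "including all patients meeting the inclusion criteria for the study as of 31 December 2024". Section 9.7.1 item 4 describes a final analysis of "all patients from the EU data sources meeting the inclusion criteria for the study as of 15 February 2025".

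**Related text.** Section 9.2 uses all available follow-up to 548 days. Section 9.7.1 keeps patients even if they have no recorded contact after inclusion. Appendix 3 grades disenrollment as *Partial* in every source.

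**The concern.** An administrative censoring date has to lie on or before the last day the data cover, and no patient should be able to enter after it. The single date in 9.3.2 falls after the US extract and before two of the stated Nordic inclusion dates.

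In the US, days after the extract hold no data and so no events. If they are counted as follow-up, rates are biased down, which is the unsafe direction in a safety study. The other censoring events give little protection, because disenrollment is incompletely recorded and lack of contact does not end follow-up.

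In the Nordic sources, an analyst cannot tell from the protocol which date closes the cohort. For Norway there are three candidates.

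**Working it through.** **Plan's own figure.** 18 months × 365.25/12 = 547.9 days, which reproduces the stated 548.

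**Calendar distances from the censoring date C = 31 December 2023**

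| Date | Source | Distance from C |
|---|---|---|
| 31 Dec 2022, US eligibility count | 9.4.2 | 365 days before |
| 15 Feb 2023, US data receipt | 6 | 319 days before |
| 4 Aug 2023, US final report | 6 | 149 days before |
| 31 Dec 2024, Norway inclusion | 9.4.1.3 | 366 days after |
| 15 Feb 2025, EU inclusion | 9.7.1 item 4 | 412 days after |

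**US, patient level.** Let E = 15 February 2023, the latest date the extract can cover if it arrives as anticipated. For index date d, observed days = min(548, E − d), and days credited under the literal rule = min(548, C − d).

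| Index date | Observed | Credited |
|---|---|---|
| 16 Aug 2021 | 548 | 548 |
| 1 Jan 2022 | 410 | 548 |
| 1 Jul 2022 | 229 | 548 |
| 31 Dec 2022 | 46 | 365 |

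Patients indexed after 16 August 2021 (E − 548 days) cannot have 548 observed days.

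**US, cohort level (illustration only).** The entry window is not in the protocol. Assume uniform entry over a window ending 31 December 2022, and ignore death and disenrollment. The unobserved share is 1 − mean observed / mean credited:

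| Window | Mean observed | Mean credited | Unobserved share |
|---|---|---|---|
| 1 year | 228.0 | 501.9 | 55% |
| 2 years | 375.1 | 524.9 | 29% |
| 3 years | 432.8 | 532.6 | 19% |
| 5 years | 478.9 | 538.8 | 11% |
| 8 years | 504.8 | 542.2 | 7% |

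A rate on that denominator would be understated by the same share. If the data stop on 31 December 2022 instead, the range is 8% (8 years) to 64% (1 year).

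**Which estimates are exposed.** Under 9.7.3, exposure person-time ends at the last prescription or dispensing plus 4 weeks. It is tied to an observed record, so it can pass the extract date by at most about 28 days. Section 9.7.3.1 adds a second denominator, all person-time through 548 days, in the text on new-onset comorbidities and concomitant medication. The full gap can enter that denominator.

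**First Nordic interim.** If data end on 31 December 2021, C lies 730 days later and never binds. Anyone indexed after 1 July 2020 (31 December 2021 − 548 days) has fewer than 548 observed days but would be credited with all 548.

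**Nordic final analysis.** Criterion 1 together with 9.3.2 makes 31 December 2023 the last possible index date. If the 2024 and 2025 dates are index-date limits, they contradict this, and a late entrant would have no follow-up time. If they are dates on which eligibility is assessed, there is no late entry, but the text does not say so. On either reading, Norway has both 31 December 2024 and 15 February 2025.

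**The case against.** **US.** Section 9.2 restricts follow-up to available data, and a competent analyst would stop at the extract. Section 9.4.2 leaves further database detail to a US SAP, where an extract end date could be set. The Section 6 dates are anticipated, and the 31 December 2022 date in 9.4.2 belongs to an expected count, not an entry limit. Sections 9.1 and 9.4 also speak of needing 548 days of data after the index date, which would remove the problem if it applied to each patient. Much of this stands: it shows a sensible intent. But the operative rule in 9.3.2 does not carry that intent out, and 9.1.1 does not make 548 days of data an inclusion criterion. The complaint concerns a date the protocol fixes itself, not a detail left to the SAP.

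**Nordic.** Criterion 1 bars entry after the study period. Sections 9.4.1.1 to 9.4.1.4 all give expected counts as of 31 December 2023, and the later dates can be read as assessment dates in delivered data. This stands as a reasonable reading. However, 9.4.1.3 uses the same *as of* wording for 31 December 2023 and for 31 December 2024, with nothing to mark a change of meaning.

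**Stronger readings a reader might infer.** One is that the US rates will be biased. That follows only if 9.3.2 is applied literally and 9.2 is ignored. A second is that every rate, proportion and duration is affected. The AESI incidence proportion has no person-time denominator, duration is built from days' supply, and AESI exposure time is largely protected. A third is that Nordic patients do enter after their own censoring date. Criterion 1 argues against that, so no share of the Nordic cohort can be put on it.

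**Conclusion.** The point holds as an internal inconsistency in the dates. The 31 December 2023 date cannot operate in the US source on the anticipated timetable, and no section lists end of data as a censoring event. The same fault applies to the first Nordic interim. For the Nordic final analysis the cut-off is contradictory, with two inclusion dates that agree neither with 31 December 2023 nor with each other.

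The downward bias is a risk under literal application, not an established result, and falls mainly on the US rates over all person-time through 548 days. The patient-level example (46 observed against 365 credited days) rests on the anticipated receipt date. The 7% to 55% range rests entirely on assumed uniform entry over 8 years to 1 year and should be read only as an illustration.

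**What to change.** - In 9.3.2, define the study period for each data source by two dates: the last permitted index date, and the last date of complete data in the extract used for that analysis (interim or final).
- Add the end of complete data in that source's extract to the censoring events.
- Carry the same definition into Figure 1 note c and inclusion criterion 1. Both rely on the study period, so the 2023 date should not simply be deleted.
- Align 9.4.1.3 and 9.7.1 item 4 to that definition, give Norway one date, and state whether each date is an index-date limit or a data-access date.

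The cost is wording in these places and somewhat smaller person-time or patient counts in some tables. No new data are needed.

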9.3.3. Covariates

When available, the following variables needed to conduct analysis for the primary and secondary research objectives will be collected. Variable availability from each country will be summarized in the SAP and is included in Appendix 3 in draft form.

Demographics and Baseline variables (Within 365 days before index date unless otherwise stated below; as depicted in Figure 1):

- 9. Patient demographics (age and sex on index date) (obtained directly from data source)
- 10. BMI, height, weight (most recent value on or before the index date) (obtained directly from data sources; BMI may be calculated if height and weight available)
- 11. Relevant comorbidities (obtained via ICD-10 codes), including:
 - 1. Weight-related comorbidities (i.e, type 2 diabetes, dyslipidaemia, hypertension)
 - 2. Neuropsychiatric conditions (mania, bipolar disorder, major depressive disorder [MDD], anorexia nervosa, bulimia)
 - 3. Uncontrolled hypertension, if possible
 - 4. Moderate or severe renal impairment
 - 5. End-stage renal disease
 - 6. Seizure disorder
 - 7. Hepatic impairment (defined by Child-Pugh score category, if available)
 - 8. Central nervous system tumour

- 12. History of, or current substance abuse/dependencies including acute opiate withdrawal (obtained via ICD-10 codes)
- 13. History of uncontrolled hypertension, seizures, bipolar disorder, MDD, anorexia nervosa, or bulimia (obtained via ICD-10 codes)
- 14. Prior medication use, including: naltrexone, bupropion, CYP2B6 inhibitors, CYP2B6 inducers, CYP2B6 substrates, CYP2D6 substrates, Monoamine oxidase inhibitors, Opioids, Opium alkaloids and derivatives and drugs that lower seizure threshold (obtained via ATC [Nordic data] or NDC [US data]) see Appendix 2 and 2A
- 15. Pregnancy status and breastfeeding status (obtained via ICD-10 codes)

All variables will be identified from the data sources outlined below using a pre-specified list of definitions per database (Appendix 3), to be defined in the SAP as final.

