8. RESEARCH QUESTIONS AND OBJECTIVES

The aim of the study is to assess the long-term (548 days) real-world utilization patterns of Mysimba/Contrave use among patients who are prescribed Mysimba/Contrave. There are no a priori hypotheses for this study.

The primary objectives of the study are:

- To describe demographic and baseline characteristics of patients initiating use of Mysimba/Contrave; and
- 2. To evaluate patterns of Mysimba/Contrave initiation and use, including number of prescriptions, number of treatment episodes and duration between prescriptions, as well as estimating the number and percentage of patients compliant and non-compliant with the SmPC.

Analysis of compliance to the labelled indication and contraindications will be adapted to the specific SmPC for the country relevant to the data source (s). Examples of non-compliance include, but are not limited to:

Use inconsistent with labelled indication:

- 1. Age <18 years
- 2. Use other than management of weight
- 3. Management of weight in a patient who does not have obesity or is not overweight and has a weight-related comorbidity
- 4. A prescribed maintenance dose other than the Mysimba/Contrave 32mg/360mg
- 5. Continued use past 16 weeks without \geq 5% weight loss

Use in patients with contraindications:

- 6. A current diagnosis of uncontrolled hypertension, seizure disorder (or history of seizures), or end-stage renal failure
- 7. A history of bipolar disorder, anorexia nervosa or bulimia
- 8. A current dependence on chronic opioids or opiate agonists (e.g., methadone)
- 9. A current state of acute opiate withdrawal
- 10. Any concomitant treatment containing bupropion, naltrexone, or a MAOI
- 11. Patients with a known central nervous system tumour

Proprietary and Confidential:

- 12. Patients undergoing acute alcohol or benzodiazepine withdrawal
- 13. Patients with severe hepatic impairment (dependent on local SmPC)

The secondary objectives of this study are:

- 1. To assess and compare the observed incidence of AESIs in usual clinical practice among users of Mysimba/Contrave compliant and non-compliant with the SmPC. AESIs include new onset of the following:
 - 1. Seizures
 - 2. Suicidality (i.e., suicidal ideation, attempted suicide or completed suicide)
 - 3. Neuropsychiatric events (i.e., mania or depression)
 - 4. Hepatotoxicity
 - 5. Severe hypersensitivity reaction
 - 6. Serotonin syndrome

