9.4.1. European Data Sources

The analysis based on the European data sources will complement an analogous methodological approach based on the data source derived from the US to inform the overall safety analysis.

After presentation of feasibility results to PRAC, the following data sources are proposed:

- 1. Denmark (Danish National Health Registries) Mysimba not reimbursed
- 2. Finland (Finnish National Registries) Mysimba reimbursed but restricted to morbidly obese
- 3. Norway (Norwegian Health Registries) Mysimba reimbursed but restricted to morbidly obese

4. Sweden (Swedish National Registries) - Mysimba not reimbursed

Currax has engaged a qualified vendor and research partner(s) who will apply for access to the licensed Nordic registry data, following Ethics Committee (EC) approval of the study protocol in each of the Nordic countries. Finalization of the protocol and particularly the SAP will necessitate consideration of specific data fields and variables that are available through this licensing process.

These national, population-based research registries capture population data, health data (including registries of hospital encounters, laboratory results (Denmark only), disease registries), death data, and socioeconomic data within each country. Records cover nearly all citizens and residents in each country throughout their time in the country. The registries have high accuracy and completeness and are maintained electronically (Laugersen et al., 2021). The registries have a strong scientific track record for accurately measuring exposure to prescription medications (Wettermark et al., 2013; Laugersen et al., 2021). Upon obtaining a separate permission, hospital records can be reviewed if necessary for the purposes of validation.

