9.6. Data Management

All de-identified (pseudonymized in Nordic countries), inpatient, outpatient and other healthcare-transactional data for patients with at least one prescription of Mysimba/Contrave will be obtained and maintained on a server by an analyst experienced in evaluating that database (patient level data will remain within each country). The data will be stored and accessed according to the sites' data privacy and security practices.

Data management and transformation to analytic datasets from the line-level data will be performed by an experienced analyst. Data extraction, curation of analytic data sets, analysis, and generation of tables and figures will be conducted in accordance with established standard operating procedures at each organization conducting data analysis. Additionally, code will be reviewed by another analyst (or the project director) adept in the coding language and analysis of the data. Face validity of descriptive statistics and incidence rates will be reviewed by the research team.

Management of the US data source will be conducted in accordance with the internal quality management system of the organization conducting the analysis, including integrated Standard Operating Procedures (SOPs) for conducting non-interventional PASS studies with secondary data. Manipulation, housing, and analysis of the US data source will occur within a managed virtual private cloud using native (i.e., secure) Amazon Web Services offerings, including a Postgres(-like) database. Statistical analyses will be conducted, principally, using SAS 9.4. If

necessary, packages from R, Python, or SPSS will be utilized – and such use will be described in the report. No individual data will be downloadable from this cloud environment. For access to the Scandinavian national patient registries, researchers or a vendor located in Scandinavia are required to access data from the registries on secure servers of registry owners.

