9.7.3. Incidence Rate of AESIs

The incidence rate of AESIs per person-years of exposure after initiation of Mysimba/Contrave will be assessed. Person-time of exposure will be calculated as the duration from the index date through the date of last Mysimba/Contrave prescription or dispensation (i.e., total treatment duration of Mysimba/Contrave), as applicable, plus 4 weeks. The number of cycles of Mysimba/Contrave during the exposure period will be summarized comparing all users, irrespective of their treatment duration status.

For each type of AESI, the crude incidence of new AESIs will be reported and the incidence proportion and 95% CI of will be estimated as the number of patients experiencing each type of event during Mysimba/Contrave exposure divided by the number of patients initiating treatment with Mysimba/Contrave. The proportion will be reported per 1,000 persons. The incidence density rate and 95% CI of AESI will be reported per 1,000 per person-years, using the sum of the person-years of the at-risk population as the denominator.

Further, clinical events of interest that might be associated with the occurrence of a potential AESI (e.g., newly initiating anti-epileptic/seizure medication, newly initiating medications indicated for mania or depression) will also be tabulated. For hepatotoxicity, liver function tests can be used (when available) in addition to diagnostic codes.

For reason(s) patients who discontinue treatment (i.e., do not refill their prescription), clinical events and health status occurring within the 90-day window prior to discontinuation will be summarized.

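### 'History of' contraindications fall under a 365-day look-back, so patients with only older codes are classed as SmPC-compliant

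*Protocol*

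**What the plan says.** **Window.** Protocol Section 9.3.3 opens its list with "Demographics and Baseline variables (Within 365 days before index date unless otherwise stated below; as depicted in Figure 1". Two items state another time point: age and sex are taken on the index date, and BMI, height and weight are the "most recent value on or before the index date". Item 13 reads "History of uncontrolled hypertension, seizures, bipolar disorder, MDD, anorexia nervosa, or bulimia (obtained via ICD-10 codes" and states none.

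**Contraindications.** Section 8 lists "A history of bipolar disorder, anorexia nervosa or bulimia" and "seizure disorder (or history of seizures" among the contraindications that make use non-compliant. Section 9.7.2 repeats them. Neither section limits how far back the history may lie, and both word other contraindications as current states.

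**Data held.** Section 9.1.1 makes 365 days of records a minimum for entry, not a ceiling. On the Nordic registries, Section 9.4.1 says: "Records cover nearly all citizens and residents in each country throughout their time in the country". Section 9.6 adds: "All de-identified (pseudonymized in Nordic countries), inpatient, outpatient and other healthcare-transactional data for patients with at least one prescription of Mysimba/Contrave will be obtained".

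**AESIs.** Section 8 describes AESIs as new onset. Section 9.7.3 defines the incidence proportion as the "number of patients experiencing each type of event during Mysimba/Contrave exposure divided by the number of patients initiating treatment with Mysimba/Contrave", and bases the incidence density on the person-years of an at-risk population that it does not define.

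**The concern.** A lifetime criterion is being measured through a one-year window. The percentage of users outside the SmPC is a primary-objective result, and the same compliant/non-compliant split carries the AESI comparison (secondary objective 1 in Section 8, objective 3 in the Synopsis). A patient with a bipolar or seizure code from two or three years before index, and nothing since, meets the contraindication as Section 8 words it but is not found under Section 9.3.3. The reported share of non-compliant users would look better than it is. The compliant group would also take in patients whose history may bear on the very events being compared, which blurs the contrast.

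A related weakness sits on the outcome side. The protocol speaks of new AESIs without saying what prior history disqualifies an event from being new, and its two incidence measures name different denominators.

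**Working it through.** **1. Which window governs item 13.** The default applies unless an item says otherwise. Items 9 and 10 do; item 13 does not. Section 9.2 calls the 365 days before index the baseline period, and footnote b of Figure 1 lists the same conditions among the baseline conditions without a separate history window. On the wording, item 13 is read over 365 days.

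**2. Direction.** Patients with a code in the last 365 days are a subset of patients with a code at any time before index. Moving from the full record to one year can therefore only remove patients from the contraindicated group. Only four histories are affected: seizures, bipolar disorder, anorexia nervosa and bulimia. Criteria based on current state, concomitant medication, age, dose or weight are not.

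**3. Size (illustration only).** The protocol gives no prevalence of these histories and no share recoded each year, so there is no figure of its own to reproduce. Inputs: N = 3,000 patients per database (Section 9.5); p = true share with such a history, assumed 1% to 5%; s = share of those with a code in the last 365 days, assumed 30% to 90%.

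Missed patients = N × p × (1 − s).

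| True history p | s = 30% | s = 50% | s = 70% | s = 90% |
|---|---|---|---|---|
| 1% (30 patients) | 21 | 15 | 9 | 3 |
| 3% (90 patients) | 63 | 45 | 27 | 9 |
| 5% (150 patients) | 105 | 75 | 45 | 15 |

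The extremes are 3,000 × 0.01 × 0.10 = 3 and 3,000 × 0.05 × 0.70 = 105, that is 0.1 to 3.5 percentage points of all users, or 10% to 70% of those with the history. A missed patient who fails another criterion stays non-compliant, so these counts are upper limits on how many cross into the compliant group.

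**4. AESI denominators.** Let h be the share of initiators who already had the condition and x the number of genuinely new cases among the rest.

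- If prior cases are kept out of the numerator, the stated proportion is x / N, whereas the risk among those able to have a first event is x / [N(1 − h)]. The ratio is 1 − h, so the proportion is understated by the fraction h.
- If prior cases are allowed in the numerator, recoded old disease is counted together with onset.

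The protocol does not say which applies, and neither gives a clean new-onset proportion. The issue concerns chronic or recurrent conditions such as seizure disorder, depression, mania and liver disease. Appendix 2, for example, lists only G40 for seizures, so without a prior-history rule a repeat code for known epilepsy cannot be told from onset. Acute events such as myocardial infarction, stroke or severe hypersensitivity are little affected.

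**The case against.** **Intent.** Item 13 repeats bipolar disorder, MDD, anorexia nervosa and bulimia from item 11. Under one common window that repetition is largely redundant, so a longer look-back may have been intended, and the Figure 1 graphic is not in the text available. This stands as doubt about intent. It does not remove the need for a change, because no longer window is written down and an SAP that follows Section 9.3.3 would carry the 365 days forward.

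**Comparability.** A uniform window is a recognised way to keep databases alike. That is a fair reason to report a 365-day version. It is weaker as a reason to make it primary, since Section 9.7.1 analyses each country separately.

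**Depth of records.** The explicit start years in Sections 9.4.1.1 to 9.4.1.4 belong to prescription registers. Diagnosis history rests on the general statements in Section 9.4.1, Section 9.6 names no look-back period for extraction, and US depth is not stated. Appendix 3 also expects bipolar disorder to be under-reported in every source. A longer look-back will therefore shrink the shortfall, not abolish it.

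**New-onset AESIs.** A reader might infer that the 365-day window also decides which AESIs are new, so that old conditions are certain to be counted as onset. The documents do not say this: the window is set for baseline variables, and AESIs are outcomes under Sections 9.3.2 and 9.7.3, where no look-back is given. Nor do they show that prior cases are already removed from the rate, because the at-risk population is undefined. A fixed percentage of dilution in the proportion cannot be claimed either, since it depends on whether prior cases leave the numerator. Section 9.7.3.1 plans sensitivity analyses around AESI definitions where data allow, and the SAP may settle the rule. What remains is that the protocol names two denominators for one concept of a new event.

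**Conclusion.** The look-back point holds. As written, the 365-day default governs the history-based contraindications, the criterion itself has no time limit, and the Nordic registries are described as holding longer records. Non-compliance on these four items is biased down, in a direction that follows from the wording alone. The size is unknown: 3 to 105 missed patients per 3,000 rests entirely on the assumed 1% to 5% history and 30% to 90% recent coding. The finding takes the protocol at its wording; if a longer window was meant, the correction is the same.

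The AESI point is secondary and narrower. For chronic or recurrent conditions, 'new' lacks a prior-history rule, and the proportion and the rate are not tied to the same people. It does not establish that old conditions will be counted as new, or by how much either measure is off.

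**What to change.** 1. In Section 9.3.3, keep 365 days as the entry minimum and as the window for current conditions and medication. For item 13, and wherever Sections 8 and 9.7.2 use a 'history of' contraindication, state that all pre-index records available in that database are used.
2. Report the look-back depth by database, and show the 365-day classification as a sensitivity analysis for both the non-compliance percentage and the AESI comparison.
3. In Section 9.7.3, for each chronic or recurrent AESI, state the look-back and define one at-risk set of patients without that condition before index. Use it for both the incidence proportion and the rate, and tabulate recurrences in patients with prior disease separately.

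The cost is protocol and SAP wording plus some programming. If the registry applications do not already cover the earlier years, they would need to. The small downside is that look-back will differ between databases and is not stated for the US; the 365-day sensitivity analysis shows how much that matters.
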